---

**The following Amendment(s) and Administrative Changes are included in this amended protocol:**

Amendment No.	Date of Amendment	Local Amendment No.	Date of local Amendment
1	_____	_____	_____
2	_____	_____	_____
3	_____	_____	_____
Administrative change No.	Date of Administrative Change	Local Administrative change No.	Date of local Administrative Change
1	_____	_____	_____
2	_____	_____	_____

## PROTOCOL SYNOPSIS

---

**An open, randomized, multicenter, phase IIIB study during 10 years to assess long-term efficacy and tolerability of esomeprazole compared to laparoscopic anti-reflux surgery in adult subjects with chronic gastro-esophageal reflux disease - LOTUS.**

---

### Study centre(s) and number of subjects planned

The number of planned subjects is 550 in 11 countries (Austria, Belgium, Denmark, France, Germany, Iceland, Italy, The Netherlands, Norway, Sweden and UK). 57-60 centres are planned with a minimum of 6 subjects per centre. All patients who enter the 5-year visit (visit 16) will be asked to participate in the prolongation of the study.

### Study period

Estimated date of first subject enrolled

Estimate date of first subject enrolled in the prolongation

Estimated date of last subject completed

### Phase of development

IIIB

## Objectives

### The primary objective of the study is:

To investigate the efficacy of long-term treatment of esomeprazole compared to anti-reflux surgery in the control of gastroesophageal reflux disease (GERD) by the assessment of time to treatment failure. (See Section 4.3 Table 3)

### Other objectives are:

- Histopathological changes in the squamous epithelium of the distal esophagus, the mucosa of the z-line and of the gastric mucosa.
- Point/periodic prevalence of endoscopic and symptomatic recurrences during 0.5 to 10 years` treatment.
- Assessment of gastrointestinal (GI) symptoms associated with GERD over time.
- In cases with Barrett`s esophagus, the extent of columnar lined esophagus.
- Per-operative events.
- Post-operative symptoms.
- Post-fundoplication complaints.
- Assessment of 24 hour pH metry, manometry and Symptom Association Probability (SAP).
- Changes in the laboratory screen variables.
- All serious adverse events and those adverse events causing premature discontinuation of study drug and/or study.
- Patient reported outcomes (PRO) assessed by QOLRAD and GSRS.

### Study design

This study is designed as a 5-year, randomized, open, parallel-group multicentre trial with a 5-year prolongation. The objectives are to estimate the efficacy and tolerability of esomeprazole compared with laparoscopic anti-reflux surgery, in a long-term treatment of adult subjects with chronic gastroesophageal reflux disease (objectively documented by endoscopy and/or abnormal 24 hour pH metry (see Section 4.3.8.)). The study will begin with a 12-week run-in period allowing recording of baseline values and responses to medical treatment with esomeprazole. This period will end with a randomization between the two therapeutic strategies.

### **Target subject population**

The target population is adult subjects with confirmed gastroesophageal reflux disease requiring long-term medical treatment. All subjects should be eligible for anti-reflux surgery. Subjects should not have more than grade B esophagitis (LA classification) or more than mild symptoms of GERD at the time of randomization into the long-term treatment phase.

### **Investigational product, dosage and mode of administration**

Esomeprazole, oral dose 20 or 40 mg daily. The healing dose is 40 mg o.d. and the maintenance dose is 20 mg o.d. Dose adjustments can be made according to subjects individual needs.

### **Comparator**

Laparoscopic anti-reflux surgery

### **Duration of treatment**

12 weeks run-in followed by a ten-year follow-up period.

### **Endpoints**

#### **-Efficacy (see Section 4.3 and Table 3)**

- Time to treatment failure where **treatment failure** is defined as;

a/ in the medical arm:

#### **Need for treatment other than esomeprazole for control of symptoms of reflux disease:**

In order to allow for a stringent assessment of treatment failure ask the following question:

*“Do you have sufficient control of your heartburn and acid regurgitation?”*

If the answer is **No**, continue with:

*“Do you need other regular drug treatment to control your symptoms?”*

If the answer to this question is **Yes** and the dose of esomeprazole is 20 mg once daily, then the dose is to be increased to 40 mg once daily. The subject will be treated with the increased dosage for 8 weeks before a second dose adjustment can be made.

If the answer to this question is **Yes** and the dose is esomeprazole 40 mg once daily, then the dose is to be changed to 20 mg twice daily. The subject will be treated with the changed dosage for 8 weeks before being classified as a treatment failure if sufficient symptom control has not been achieved.

If the answer to this question is **Yes** and the dose is 20 mg twice daily, then the subject is a **treatment failure and will be withdrawn.**

b/ In the surgical arm:

**Need for medical treatment for control of symptoms from reflux disease:**

In order to allow for a stringent assessment of treatment failure ask the following question:

*“Do you have sufficient control of your heartburn and acid regurgitation?”*

If the answer is **No**, continue with:

*“Do you need other regular drug treatment to control your symptoms?”*

If the answer to this question is **Yes** the subject has to be classified as a **treatment failure and will be withdrawn.**

Furthermore, the subject will also be regarded as a **treatment failure** if the following occurs;

- Post-operative - post-fundoplication complaints requiring further medical actions to control symptom burden.
- Per-operative death
- Post-operative death within 30 days after surgery
- Dysphagia requiring further treatment. In case of esophageal stenosis, one dilatation is allowed.

**Other efficacy endpoints**

- Histopathological variables
- Scores of symptom variables.
- Endoscopic assessments.
- Assessment of 24 hr pH metry and SAP.

**Safety (see Section 4.4 Table 4)**

- Laboratory variables.
- All serious adverse events and those adverse events causing premature discontinuation of study drug and/or study.

**Quality of Life (see Section 4.5 Table 5)**

- Patient-reported outcomes assessed by GSRS and QOLRAD

**Statistical methods**

The treatment arms will be compared regarding time to evidence of treatment failure by a logrank test. The comparison will be made for an ITT population.

Other endpoints will be analysed descriptively.

## LIST OF ABBREVIATIONS AND DEFINITION OF TERMS

The following abbreviations and specialist terms are used in this study protocol.

Abbreviation or specialist term	Explanation
AE	Adverse event (see definition in Section 4.4.2.1)
ALAT	Alanine aminotransferase
ASA	Acetylsalicylic acid
ASAT	Aspartate aminotransferase
b.i.d.	Twice daily
CLE	Columnar lined esophagus
CRF	Case Report Form
CRO	Contract Research Organisation
ECL-cells	Enterochromaffin-like cells
FSI	First Subject In
GCP	Good Clinical Practice
GERD	Gastroesophageal reflux disease
GI	Gastro-intestinal
GSRS	Gastro-intestinal Symptoms Rating Scale
H.p.	Helicobacter pylori
H 2 RA	H 2 receptor antagonist
hr	hour
HRQL	Health-Related Quality of Life
ICH	International Conference on Harmonisation
IEC	Independent Ethics Committee
International principal investigator	The investigator who leads the whole study.
IRB	Institutional Review Board
ITT	Intention To Treat
LSI	Last Subject In
LSO	Last Subject Out
MedRA	Medical Dictionary for Regulatory Activities
mg	milligram
NB	nota bene
NSAID	Non-steroid anti-inflammatory drugs

OAE	Other significant adverse event (i.e., an adverse event of special interest in this clinical development; see definition in Section 4.4.2.1). The classification of OAEs will be made by AstraZeneca drug safety physicians when the study has been completed.
o.d.	once daily
OTC	Over-the-counter
PP	Per protocol
PPI	Proton pump inhibitor
Principal investigator	The investigator who leads the study conduct at an individual study centre. Every study centre has a principal investigator.
p.r.n.	pro re nata
PRO	Patient-Reported Outcomes
QOLRAD	Quality Of Life in Reflux And Dyspepsia
RBC	Red blood cell count
RE	Reflux esophagitis
SAE	Serious adverse event (see definition in Section 4.4.2.1).
SAP	Symptom Association Probability
WBC	White Blood Cells
WHO	World Health Organisation

## 1. INTRODUCTION

### 1.1 Background

Gastroesophageal reflux disease (GERD) is a common health problem causing a variety of symptoms, the most predominant being heartburn. Studies suggest that 20-40% of the adult population at some time experience heartburn, and approximately 7% of these subjects have this symptom every day (Spechler SJ 1992). In most subjects GERD symptoms are caused by acidic gastric juice refluxing into the esophagus. The severity of heartburn is determined by a number of factors of which the amount of acid reflux is one (Lind T et al 1997).

In about half of the subjects suffering from symptoms of GERD, endoscopy will demonstrate signs of esophageal lesions of at least grade A (Los Angeles classification). Despite symptoms of similar severity and intensity the remainder of GERD subjects have normal endoscopic findings, i.e. non-erosive disease (Spechler SJ 1992, Jones RH et al 1995, Heading RC 1989, Johnson F et al 1987). Of functional importance is, however that GERD symptoms have significant negative impact on health-related quality of life (Carlsson R et al 1998), irrespective of whether erosive esophagitis is present or not.

GERD is a chronic relapsing disease. The two main long-term treatment alternatives in use are medication and surgery.

Medical treatment today is based on proton pump inhibitors (PPIs) administration, e.g. omeprazole (Dent J et al 1999) to reduce gastric acid secretion and normalise acid reflux into the esophagus, thereby healing erosive esophagitis and relieving symptoms.

A recent long-term study comparing omeprazole maintenance treatment with the conventional open fundoplication operation has shown both strategies to be effective (Lundell L et al 2000).

Esomeprazole is a further development of the original omeprazole (PPI) concept. Esomeprazole offers a more profound and longer lasting inhibition of gastric acid secretion during a 24-hour period than omeprazole and the interindividual variation in intragastric acidity is reduced. Clinical studies have shown esomeprazole, given in the doses recommended, to be more effective than omeprazole, both in terms of healing esophagitis and in relieving reflux symptoms.

Anti-reflux surgery has undergone technical changes during the last decade. The most commonly favoured operation today is a laparoscopic approach. The laparoscopic operation seems to offer a less troublesome and a shorter post-operative convalescent period compared to the traditional open technique (Lundell L 2000).

### 1.2 Rational for this study

This study will compare the two main long-term therapeutic options in GERD, an up-to-date surgical therapy with modern medical treatment, over a ten year period. Valuable information

will be gained for the long-term efficacy and safety of esomeprazole maintenance treatment in GERD.

## **2. STUDY OBJECTIVES**

### **2.1 Primary objective**

The primary objective of the study is to investigate the efficacy of long-term treatment of esomeprazole compared to laparoscopic anti-reflux surgery in the control of gastroesophageal reflux disease by the assessment of time to treatment failure (see Section 4.3 and Table 3).

### **2.2 Other objectives**

Other objectives of the study are to assess;

#### Efficacy measurements (see Section 4.3 and Table 3)

- Histopathological changes in the squamous epithelium of the distal esophagus, the mucosa of the z-line and in the gastric mucosa.
- Point/periodic prevalence of endoscopic and symptomatic recurrences during 0.5 to 10 years` treatment.
- GI symptoms associated with GERD.
- In cases of Barrett` s esophagus, the extent of columnar lined esophagus
- Per-operative events
- Post-operative symptoms and post-fundoplication complaints
- Assessment of 24hr pH metry, manometry and SAP (Symptom Association Probability)

#### Safety measurements (see Section 4.4 Table 4)

- Changes in the laboratory screen variables.
- All serious adverse events and those adverse events causing premature discontinuation of study drug and/or study.

#### Quality of Life

- Patient-reported outcomes assessed by GSRS and QOLRAD (see Section 4.5. Table 5)

### 3. STUDY PLAN AND PROCEDURES

#### 3.1 Overall study design and flow chart

This study is designed as a 5-year, randomized, open, parallel-group multicentre trial with a 5-year prolongation with the objectives to estimate the efficacy and tolerability of esomeprazole compared with anti-reflux surgery, in a long-term treatment of adult subjects with confirmed, symptomatic gastroesophageal reflux disease with or without esophagitis (objectively documented by endoscopy and abnormal 24 hour pH metry). All subjects should be eligible for surgery.

The study will begin with a 12-week run-in period enabling the recording of baseline values and responses to medical treatment with esomeprazole 40 mg o.d. This period will end with a randomization into the 10-year study period. All subjects should have the need for continuous treatment to control reflux and be eligible for anti-reflux surgery. Subjects should not have more than LA grade B endoscopic-visualized mucosal breaks or more than mild symptoms of GERD prior randomization and should have responded to esomeprazole treatment in the 12-week run-in period.

The 10-year study period consists of 2 treatment arms, medical treatment (esomeprazole, start dose is 20 mg o.d.) and anti-reflux surgery (laparoscopic fundoplication). Subjects willing to accept randomization to either surgery or long-term medical treatment will receive treatment according to a randomization list.

*Helicobacter pylori* (*Hp*) status will be assessed based on biopsy material.

In case of confirmed peptic ulcer disease and positive *Hp* testing eradication therapy should be given prior to enrolment. Subject should not be enrolled within 3 months after therapy.

In case of a first episode of peptic ulcer disease during the 10-year study period and confirmed positive *Hp* testing eradication therapy is allowed.

In all other cases of *Hp* infection not associated with peptic ulcer disease eradication therapy is not allowed.

The planned number of subjects is 550 randomized in 11 countries, with at least 6 subjects per centre.

Visits 1, 2, 3, 4, 5, 6, 7, 8, 12, 16, 31, 33, 35, 37 and 39 will be regular visits with the investigator and visits 9, 10, 11, 13, 14 and 15 may be done by the study nurse.

During the 5-year prolongation, all subjects will visit the hospital after 6, 7, 8, 9 and 10 years for assessments. At 5.5, 6.5, 7.5, 8.5 and 9.5 the subjects will have a telephone visit (hospital visit optional). The hospital visit should be done by the investigator and the telephone should preferably be done the investigator.

Randomized subjects who have discontinued but not withdrawn their informed consent will be followed-up by a phone call from the investigators at 5 and 10 years after randomization. This will also be applicable for subjects who discontinue during the prolonged period. The follow-up phone call consists of questions about the subject's surgery related to GERD, present medical treatment of GERD and present symptom load. For more information see Appendix P to the amendment

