### **3.3.5 Discontinuation of subjects from treatment or assessment**

#### **3.3.5.1 Criteria for discontinuation**

Subjects may be discontinued from study treatment and assessments at any time, at the discretion of the investigator(s). A subject may, however, continue the study under exceptional circumstances (e.g. if continuation of study treatment or follow-up actions are necessary for the subjects safety and well-being, and the continuation of the study is not expected to be associated with any risk or discomfort for the subject). Specific reasons for discontinuing a subject from this study are:

1. Withdrawal of informed consent
2. Unwillingness to continue the study or lost to follow-up.
3. Any unacceptable adverse event, including laboratory result or physical findings, as judged by the investigator
4. Any “alarm symptoms” which, in the investigator’s judgement, requires treatment outside this protocol.
5. Continuous need for/intake of drugs listed under Section [3.3.4](#) criteria 7.
6. Protocol non-compliance as judged by the investigator
7. Classified as treatment failure
8. Pregnancy
9. Incorrect enrolment or randomization of subject
10. Other reason specified by the investigator.

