**Need for medical treatment for control of symptoms from reflux disease:**

In order to allow for a stringent assessment of treatment failure ask the following question:

*“Do you have sufficient control of your heartburn and acid regurgitation?”*

If the answer is **No**, continue with:

*”Do you need other regular drug treatment to control your symptoms?”*

If the answer to this question is **Yes** the subject has to be classified as a **treatment failure and will be withdrawn**.

Furthermore, the subject will also be regarded as a **treatment failure** if the following occurs;

- Post-operative - post-fundoplication complaints requiring further medical actions to control symptom burden.
- Per-operative death
- Post-operative death within 30 days after surgery
- Dysphagia requiring further treatment. In case of esophageal stenosis, one dilatation is allowed.

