#### 4.4.2.2 Recording of adverse events

SAEs and AEs causing premature discontinuation of study drug and/or study will be recorded retrospectively by the investigator in the Case Report Form at visit 2 and the following visits. If any SAE or AE causing premature discontinuation of study drug and/or study are ongoing at the subjects last visit in the study, they must be followed up after 2 to 4 weeks and thereafter as long as medically indicated. This can be done either as an extra visit to the clinic or by written or verbal contact with the subject.

Spontaneously reported SAEs and AEs causing premature discontinuation of study drug and/or study, objective findings and observations, and SAE and AEs causing premature discontinuation of study drug and/or study reported in response to the standardized question “Have you had any health problems since the previous visit?” will be recorded in the CRF. Start and stop date (or marked as ongoing), outcome, maximum intensity, seriousness, and action taken with regard to investigational product and if the AE caused subject to discontinue the study will be recorded. Maximum intensity will be rated according to the following scale:

- |              |  |
|--------------|--|
| 1 = Mild     | - awareness of sign or symptom, but easily tolerated                 |
| 2 = Moderate | - discomfort sufficient to cause interference with normal activities |
| 3 = Severe   | - incapacitating, with inability to perform normal activities        |

It is important to distinguish between serious and severe AEs. Severity is a measure of intensity whereas seriousness is defined by the criteria in Section 4.4.2.1. An AE of severe intensity need not necessarily be considered serious. For example, nausea, which persists for several hours, may be considered severe nausea, but not a SAE. On the other hand, a stroke which results in only a limited degree of disability may be considered a mild stroke but would be a SAE.

Abnormal test results from laboratory investigations or endoscopy investigations (including biopsies) that meet any criteria of an SAE must be reported in accordance with the SAE reporting procedures (see Section 4.4.2.3).

Symptoms included in the efficacy variables

- Section 4.3.5.1 GERD symptoms (i.e. heartburn, acid regurgitation, dysphagia)
- Section 4.3.5.1. other GI symptoms (i.e. epigastric pain, flatulence, bloating, ability to vomit, ability to belch, diarrhoea)

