## **6. STATISTICAL METHODS AND DETERMINATION OF SAMPLE SIZE**

### **6.1 Determination of sample size**

The true rate of treatment successes (i.e. subjects who have not experienced treatment insufficiency within 5 years) is assumed to be at least 70% for both treatments. With 275 subjects on each treatment the true difference between treatment is, with a probability of 95%, not going to differ by more than 8 percentage points from the observed difference.

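### No scheduled enquiry for new SAEs is described after the discontinuation visit, so safety after treatment failure is not systematically observed in either arm

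*Protocol*

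**What the plan says.** **Failure leads out of the study.** In both arms, a subject who fails on the symptom questions is a "treatment failure and will be withdrawn" (Section 4.1). Section 3.3.5.1 lists "Classified as treatment failure" as reason 7 for discontinuation, and discontinuation reaches beyond treatment: "Subjects may be discontinued from study treatment and assessments at any time".

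**SAEs are sought at visits.** Section 3.1 ties recording to the study visits, and Section 3.3.5.4 adds the discontinuation visit. Under Section 4.4.2.2, if SAEs are "ongoing at the subjects last visit in the study, they must be followed up after 2 to 4 weeks", and then for as long as there is a medical reason. Section 4.4.2.3 requires any SAE that comes to the investigator's notice during the study to be reported.

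**Later contact is the call.** Discontinued subjects who have kept their consent are telephoned at years 5 and 10. Section 3.1 gives the content as "surgery related to GERD, present medical treatment of GERD and present symptom load" and refers to Appendix P for more.

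**Continuing subjects are handled differently.** In Table 2, adverse events are the one item marked at the half-yearly telephone visits of the prolongation.

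**Analysis.** Table 4 summarises how many subjects have SAEs, descriptively and for the safety population.

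**The concern.** The protocol sets out to estimate tolerability as well as efficacy against surgery over ten years (Sections 3.1 and 3.2). Structured recording of post-operative events ends at about 30 days (Section 4.3.7), so later surgical harm is seen mainly through SAEs. A subject who fails after surgery still has the fundoplication, and a subject who fails on esomeprazole may go on to surgery. For both, the scheduled search for SAEs ends with the discontinuation visit and the follow-up of events already under way.

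After that, an SAE enters the data only if the investigator happens to hear of it. That is likely to vary with whether the site still treats the subject. If one arm fails more often, it also has less systematically observed time. A table that counts subjects with SAEs, with no regard to observation time, would then flatter that arm.

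**Working it through.** **Inputs from the protocol (Section 6.1).** The 5-year success rate "is assumed to be at least 70% for both treatments". Each arm has 275 subjects, and at a 95% level the plan promises an accuracy worded as "not going to differ by more than 8 percentage points from the observed difference". Total 2 × 275 = 550 subjects; planned follow-up 10 years, so 5,500 person-years.

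**The plan's own figure.** Half-width = 1.96 × √(2 × 0.70 × 0.30 / 275) = 0.0766, or 0.0766 + 1/275 = 0.0802 with a continuity correction. Both round to 8 points, so the statement reproduces. It concerns efficacy precision and is used here only to confirm how the 70% and 275 are meant.

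**Assumptions for the size of the gap.** Time to failure has a constant hazard λ = −ln(S5)/5, where S5 is the 5-year success rate. Every failure is withdrawn at failure. Deaths and other discontinuations are ignored. Two patterns after year 5 are taken: the hazard continues, or no further failures occur.

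**At the 70% floor.**
- λ = 0.3567/5 = 0.07133 per year.
- Failures by year 5: 0.30 × 550 = 165. By year 10 with continuing hazard: S(10) = 0.70² = 0.49, so 0.51 × 550 ≈ 280.
- Continuing hazard: mean failure-free time = (1 − 0.49)/0.07133 = 7.15 years. Time after failure = 2.85 years per subject, × 550 ≈ 1,568 person-years, or 28.5% of 5,500.
- No failures after year 5: 0.30/0.07133 + 5 × 0.70 = 4.21 + 3.50 = 7.71 years. Time after failure = 2.29 years per subject, about 1,262 person-years, or 22.9%.

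**At better success (assumed values, same formulas).**

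| 5-year success | Hazard continues | No failures after year 5 |
|---|---|---|
| 70% | 28.5% (1,568) | 22.9% (1,262) |
| 80% | 19.3% (1,063) | 15.2% (835) |
| 90% | 9.8% (541) | 7.5% (415) |

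Cells show the share of planned person-time after failure (person-years, both arms at the same rate).

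**What unequal failure would do (illustration).** With continuing hazard, mean failure-free time is 7.15 years at 70%, 8.07 at 80% and 9.02 at 90%. Suppose the true SAE rate is the same in both arms, unrelated to failure, and low enough for the count of subjects to follow person-time. An arm at 70% beside one at 90% would then show 1 − 7.15/9.02 ≈ 21% fewer subjects with SAEs. At 80% beside 90% the figure is 1 − 8.07/9.02 ≈ 11%. With more frequent events the distortion would be smaller.

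**The case against.** Four stronger readings are tempting, and the protocol does not support them.

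- *SAE collection stops at withdrawal.* A reader might infer this from the rule on ongoing events, but no section says so. The SAE definition in Section 4.4.2.1 covers every study phase including follow-up, and the reporting duty in Section 4.4.2.3 is not limited to subjects on treatment. An SAE mentioned during a call would arguably be reportable. What remains is that neither provision schedules an enquiry.
- *The calls do not ask about deaths, admissions or cancer.* This cannot be confirmed, because the questions are in Appendix P. Section 3.1 is worded as a description of what the call consists of, and names only three GERD topics, but it is a summary.
- *Failures are left out of the safety comparison.* They are not. Section 6.2.1 does not exclude them from the safety population, the discontinuation visit records their SAEs, and ongoing events are followed. Only their later time is unsolicited.
- *More than a quarter of the safety data is lost.* The 28.5% rests on a floor for success and on a hazard carried unchanged to year 10. It is also a share of person-time and does not count missed events.

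There is also a fair case that the present design is defensible. Safety is descriptive, and Table 4 directs its purpose at adverse reactions during esomeprazole treatment. After discontinuation, subjects receive usual care, so later events reflect mixed treatments. Reoperation is partly caught by the question on GERD surgery, and person-year reporting could be left to the SAP. These points limit the weight of the concern. They do not remove it, since comparative tolerability is a stated aim and a descriptive count misleads just as readily when observation time differs.

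**Conclusion.** The point holds as a gap in planned data collection. After the discontinuation visit and the follow-up of ongoing events, the protocol describes no scheduled enquiry for new SAEs in either arm, although it makes one by telephone for continuing subjects. The time affected is about 23-29% of planned 10-year person-time at 70% success, and about 8-19% at an assumed 80-90%. These figures rest on the constant-hazard assumption and count failures only; other discontinuations would add to them. The comparison is affected if failure rates differ between the arms; the protocol gives no figure for such a difference, so the size and direction of any bias are unknown. If Appendix P already asks about SAEs and deaths, what remains is to say so in Section 3.1 and to report by observation time. This is a worthwhile, inexpensive improvement and does not undermine the primary analysis.

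**What to change.** 1. State in Section 3.1, and in Appendix P if it is not already there, that the calls at years 5 and 10 also record, each with date: vital status and cause of death; hospital admissions and other SAEs; and upper-GI malignancy or dysplasia. Add a date to the existing question on GERD surgery, which partly covers reoperation. Name a source for vital status where the subject cannot be reached.
2. Say in Section 4.4.2 how new SAEs learned of after discontinuation are recorded.
3. In Table 4 or the SAP, report SAEs and deaths by allocated arm per person-year of observation, with on-study and post-discontinuation events shown separately.

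The cost is a few questions in calls already scheduled, a small form and consent update, and one further table. Recall over up to five years will be imperfect, more so for minor admissions than for deaths, cancers or operations. Events after discontinuation will reflect mixed treatments, which is why they should be shown apart. Subjects who withdraw consent remain outside the calls.
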